4.2.1 Adverse events

Adverse events (AE) will be coded using the MedDRA Version 18 and will be classified by Preferred Term (PT) and System Organ Class (SOC).

A Treatment Emergent Adverse Events (TEAE) will be defined as any adverse event that occurs from the time of first study treatment dose administered to the patient until last study visit.

An SAE is defined as an AE that meets one of the following conditions:

- Death.
- Life threatening event (defined as any AE that places the patient, in the view of the Investigator, at immediate risk of death from the event as it occurred, i.e., it does not include an event that had occurred in a more severe form, might have caused death).
- An event requiring inpatient hospitalization or prolongation of existing hospitalization during the period of protocol defined surveillance.
- Results in a persistent or significant disability/incapacity.
- Congenital anomaly or birth defect in the offspring of a study participant.
- Any other important medical event that may not result in death, be life threatening, or require hospitalization, may be considered a serious adverse experience when, based upon appropriate

Statistical Analysis Plan

Study Name: IFN-K-002

SAP version & date: v4, 18/Jun/2018

medical judgment, the event may jeopardize the patient and may require medical or surgical intervention to prevent one of the outcomes listed above. Examples of such medical events include allergic bronchospasm requiring intensive treatment in an emergency room or at home, blood dyscrasias or convulsions that do not result in inpatient hospitalization, or the development of drug dependency or drug abuse.

Tolerability/safety will be assessed over the 36 weeks study period. The analysis will focus on:

- Occurrence and intensity of any solicited local and systemic reactions during a 7-day follow-up period (i.e. day of study product administration and 6 subsequent days) after each IFN-K or placebo dose
- Occurrence, intensity and relationship of unsolicited AEs occurring throughout the study period
- Occurrence, intensity and relationship of all SAEs occurring throughout the study period
- Rate and severity of viral infections
- Flares (time of occurrence in relation to product administration)

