5.2.5.2 Adverse events

Adverse event tabulations:

Tabulation of adverse events will present for each cell the following information: number of patients with at least one occurrence of the event, corresponding percentage and number of events (if relevant).

The following tables will be produced for the Safety population as well as by treatment group:

The definition of TEAEs is described in section 4.2.1.

The following period will be defined:

- before first dose
- [1st dose; 2nd dose[
- [2nd dose; 3rd dose[
- [3rd dose; 4th dose[
- [4th dose; 5th dose[
- [5th dose; Week 36]
- [Last dose; Week 36/Early Termination] (for AE which cannot be classified in the previous periods due to dose not received or premature study termination)

Summary table of adverse events (Statistical Table 14.3.2):

- Any AE
- Any TEAE
- Any TEAE by period
- Any TEAE leading to study treatment temporarily discontinuation
- Any TEAE leading to study treatment permanent discontinuation
- Any TEAE of intensity severe or more
- Any TEAE considered related to the study treatment (possibly or probably related)
- Any SAE
- Any SAE by period
- Any Treatment Emergent SAE (TESAE)
- Any TESAE leading to study treatment temporarily discontinuation
- Any TESAE leading to study treatment permanent discontinuation
- Any TESAE considered related to the study treatment (possibly or probably related)
- Any TESAE of intensity severe or more

Statistical Analysis Plan

Study Name: IFN-K-002

SAP version & date: v4, 18/Jun/2018

- Death

Detailed Tables:

All tables listed below will be presented by period (except if otherwise specified):

- Solicited local reactions during a 7-day follow-up period after each study product administration by SOC and PT (Statistical Tables 14.3.3.1 to 14.3.3.6)
- Solicited local reactions during a 7-day follow-up period after each study product administration by SOC, PT and intensity (Statistical Tables 14.3.4.1 to 14.3.4.6)
- Solicited systemic reactions during a 7-day follow-up period after each study product administration by SOC and PT (Statistical Tables 14.3.5.1 to 14.3.5.6)
- Solicited systemic reactions during a 7-day follow-up period after each study product administration by SOC, PT and intensity (Statistical Tables 14.3.6.1 to 14.3.6.6)
- TEAEs by SOC and PT (Statistical Tables 14.3.7.1 to 14.3.7.6)

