- TEAEs by SOC, PT and status of IFN α neutralizing antibodies (positive/negative) at time of event (only on patients IFN-K treated) (Statistical Tables 14.3.7.7 to 14.3.7.10)
- TEAEs by SOC, PT and relationship (Statistical Tables 14.3.8.1 to 14.3.8.6)
- TEAEs by SOC, PT and intensity (Statistical Tables 14.3.9.1 to 14.3.9.6)
- TEAEs leading to permanent study treatment discontinuation by SOC and PT (Statistical Table 14.3.10) (only throughout the study)
- SAEs by SOC and PT (Statistical Tables 14.3.11.1 to 14.3.11.7)
- SAEs by SOC, PT and status of IFN α neutralizing antibodies (positive/negative) at time of event (only on patients IFN-K treated) (Statistical Tables 14.3.11.8 to 14.3.11.11)
- SAEs by SOC, PT and relationship (Statistical Tables 14.3.12.1 to 14.3.12.7)
- SAEs by SOC, PT and intensity (Statistical Tables 14.3.13.1 to 14.3.13.7)
- SAEs leading to permanent study treatment discontinuation by SOC and PT (Statistical Table 14.3.14)

The following rules will be applied to analyze the occurrence of AE according to the status of IFN α neutralizing antibodies (positive/negative):

- For adverse event which occurred between dose 1 and dose 3 included, status of neutralizing capacity will not be assessed
- For adverse event which occurred between 3rd dose (excluded) and Visit 6 (included), status of neutralizing capacity at visit 6 will be used
- For adverse event which occurred between Visit 6 (excluded) and Visit 9 (included), status of neutralizing capacity at visit 9 will be used
- For adverse event which occurred between Visit 9 (excluded) and Visit 12 (included), status of neutralizing capacity at visit 12 will be used

Statistical Analysis Plan

Study Name: IFN-K-002

SAP version & date: v4, 18/Jun/2018

Statistical Analysis Plan

Study Name: IFN-K-002

SAP version & date: v4, 18/Jun/2018

Adverse events listings:

All adverse events (including solicited local and systemic reactions) recorded during the study will be presented in Listings. The following information (if available) will be included in the listings (non-exhaustive list):

- Patient identifier
- Age, Ethnic origin (see section 9 Derived data), gender, weight
- The adverse event (System organ class, preferred term, reported term)
- Start date, end date, duration, period
- Severity (e.g., mild, moderate, severe)
- Seriousness (serious/non-serious)
- Action taken
- Outcome
- Relatedness assessment

Listings will be provided for:

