14.3.5.6	Solicited systemic reactions during a 7-day follow-up period after each study product administration by SOC and PT - Period [Last dose; Week 36/Early Termination]		X			
14.3.6.1	Solicited systemic reactions during a 7-day follow-up period after each study product administration by SOC, PT and intensity - Period [1st dose; 2nd dose[X			
14.3.6.2	Solicited systemic reactions during a 7-day follow-up period after each study product administration by SOC, PT and intensity - Period [2nd dose; 3rd dose[X			
14.3.6.3	Solicited systemic reactions during a 7-day follow-up period after each study product administration by SOC, PT and intensity - Period [3rd dose; 4th dose[X			

Statistical Analysis Plan

Study Name: IFN-K-002

SAP version & date: v4, 18/Jun/2018

Number	Title	Screened	SAF	FAS	PP	Other
14.3.6.4	Solicited systemic reactions during a 7-day follow-up period after each study product administration by SOC, PT and intensity - Period [4th dose; 5th dose[X			
14.3.6.5	Solicited systemic reactions during a 7-day follow-up period after each study product administration by SOC, PT and intensity - Period [5th dose; Week 36]		X			
14.3.6.6	Solicited systemic reactions during a 7-day follow-up period after each study product administration by SOC, PT and intensity - Period [Last dose; Week 36/Early Termination]		X			
14.3.7.1	TEAEs by SOC and PT - Period [1st dose; 2nd dose[X			
14.3.7.2	TEAEs by SOC and PT - Period [2nd dose; 3rd dose[X			
14.3.7.3	TEAEs by SOC and PT - Period [3rd dose; 4th dose[X			
14.3.7.4	TEAEs by SOC and PT - Period [4th dose; 5th dose[X			
14.3.7.5	TEAEs by SOC and PT - Period [5th dose; Week 36]		X			
14.3.7.6	TEAEs by SOC and PT - Period [Last dose; Week 36/Early Termination]		X			
14.3.7.7	TEAEs by SOC, PT and status of anti-IFN α neutralizing antibodies and anti-IFN α binding antibodies at time of event - Period [3rd dose; 4th dose[X			
14.3.7.8	TEAEs by SOC, PT and status of anti-IFN α neutralizing antibodies and anti-IFN α binding antibodies at time of event - Period [4th dose; 5th dose[X			
14.3.7.9	TEAEs by SOC, PT and status of anti-IFN α neutralizing antibodies and anti-IFN α binding antibodies at time of event - Period [5th dose; Week 36]		X			
14.3.7.10	TEAEs by SOC, PT and status of anti-IFN α neutralizing antibodies and anti-IFN α binding antibodies at time of event - Period [Last dose; Week 36/Early Termination]		X			
14.3.8.1	TEAEs by SOC, PT and relationship - Period [1st dose; 2nd dose[X			

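### Apart from events that ended treatment, TEAEs and SAEs by SOC/PT are tabulated only by dosing period, so Week 0–36 incidence per term by arm has no table and the viral-infection endpoint has no dedicated one

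*SAP*

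**What the plan says.** SAP 4.2.1 sets the safety assessment over the 36-week study. Among its stated focuses are "Occurrence, intensity and relationship of unsolicited AEs occurring throughout the study period" and "Rate and severity of viral infections". The viral-infection item is also a safety endpoint in Protocol 13.4.

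SAP 5.2.5.2 then defines the outputs. Each cell holds the "number of patients with at least one occurrence of the event, corresponding percentage and number of events (if relevant". On presentation by arm it says: "The following tables will be produced for the Safety population as well as by treatment group". It defines a pre-dose period, five intervals running from one dose to the next or to Week 36, and a residual interval for events that fit none of these because a dose was missed or the patient left early. The rule for the detailed tables is: "All tables listed below will be presented by period (except if otherwise specified". Examples are "TEAEs by SOC and PT (Statistical Tables 14.3.7.1 to 14.3.7.6" and "SAEs by SOC and PT (Statistical Tables 14.3.11.1 to 14.3.11.7". In SAP 10.1 the last of the general TEAE tables is still a period table: "TEAEs by SOC and PT - Period [Last dose; Week 36/Early Termination".

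Protocol 13.9.5 plans to summarise the frequency and severity of all AEs for each arm, and presents summaries by number of doses as an addition. SAP 7.3, which records departures from the protocol on adverse events, mentions only the dropped analysis of reactions at one hour.

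**The concern.** A safety reader's basic question is how many patients in each arm had a given event between first dose and Week 36. The SAP names that as its endpoint, yet the planned displays answer a different question: how many patients had the event in each of several intervals of unequal length. Patient counts do not add up across intervals, so the by-arm comparison for each term would have to be assembled from listings after unblinding, with no agreed rules. The viral-infection endpoint has a further gap. Viral infections are spread over many preferred terms, so even a whole-study SOC/PT table would not give a pooled rate unless the grouping were defined.

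**Working it through.** The plan gives no figure to reproduce. The check is a count of tables, then a demonstration of what period tables can and cannot tell a reader.

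**1. Table count (SAP 5.2.5.2 against SAP 10.1)**

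| Content | Tables | Periods | Whole-study version |
|---|---|---|---|
| TEAE by SOC/PT | 14.3.7.1–6 | six post-dose | none |
| TEAE by relationship | 14.3.8.1–6 | six post-dose | none |
| TEAE by intensity | 14.3.9.1–6 | six post-dose | none |
| SAE by SOC/PT | 14.3.11.1–7 | pre-dose plus six | none |
| SAE by relationship | 14.3.12.1–7 | pre-dose plus six | none |
| SAE by intensity | 14.3.13.1–7 | pre-dose plus six | none |

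Total: 3 × 6 + 3 × 7 = 39 period tables and no whole-study table. The numbering is closed, with every number tied to one period. The antibody-status tables (14.3.7.7–10 and 14.3.11.8–11) are also by period and cover IFN-K patients only. Tables 14.3.10 and 14.3.14 are not split by period but are restricted to events that ended treatment permanently. Table 14.3.2 is not restricted to a period for its main rows, but does not go down to terms.

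**2. What can be recovered from the period tables**

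Let n_k be the number of patients in an arm with a given term in period k. The number N with that term at any time satisfies

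max(n_k) ≤ N ≤ Σ n_k

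The lower limit applies if the same patients recur, and the upper limit if nobody does. Illustration with assumed counts of 2, 3, 6, 8 and 8 in the five main intervals, none in the residual interval, and 89 patients (the target per arm in Protocol 8.1, not the realised safety set):

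- lower limit: 8/89 = 9.0%
- upper limit: 27/89 = 30.3%

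**3. How a term looks when it is split**

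Doses at Weeks 0, 1, 4, 12 and 24 give intervals of 1, 3, 8, 12 and 12 weeks. Assume a constant hazard, full dosing on schedule and a 36-week incidence p. The incidence in an interval of L weeks is 1 − (1 − p)^(L/36).

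| p over 36 weeks | Interval percentages | Largest | Sum |
|---|---|---|---|
| 10% | 0.3, 0.9, 2.3, 3.5, 3.5 | 3.5% | 10.4% |
| 20% | 0.6, 1.8, 4.8, 7.2, 7.2 | 7.2% | 21.6% |
| 30% | 1.0, 2.9, 7.6, 11.2, 11.2 | 11.2% | 34.0% |

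For example, at p = 20% and L = 12: 1 − 0.8^(1/3) = 7.2%. No single table shows anything near 20%, and adding the tables overshoots it. These rates are assumptions; the documents give none.

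**4. Viral infections**

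The endpoint is named in Protocol 13.4 and SAP 4.2.1. No entry in SAP 10.1 pools viral terms. The only infection-specific table, 14.3.19 (described in SAP 5.2.5.3), covers severe infections by lymphocyte count at Visit 2. It is not limited to viral infections and leaves out milder ones.

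**5. Protocol against SAP**

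In Protocol 13.9.5 the summary per arm is the main item and the dose-based summary is extra. In the SAP, at term level, only the interval version remains. SAP 7.3 does not list this among the changes.

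**The case against.** The strongest reply is that nothing is lost. Listings 16.2.7.3 and 16.2.7.4 hold the adverse events by patient, with term, dates, period and severity, so 36-week counts can be derived at any time. Table 14.3.2 already gives by-arm totals for any TEAE, any SAE, related events, severe events and deaths. The protocol's commitment to a summary per arm has not been withdrawn, so this may be an oversight in the table list rather than a deliberate analysis choice. The event-count part of each cell, unlike the patient count, can be added over periods.

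All of that stands, and it rules out three stronger readings that a reader might infer:

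- That whole-study incidence per term could never be reported. It could, from the listings; it is only not tabulated.
- That viral infections would go unreported. Those recorded as AEs would appear by preferred term and intensity in the period tables and in the listings. What is missing is a dedicated table that pools them.
- That the documents rank viral infection as the leading mechanism-based risk. Protocol 5.6 raises the question but says it need not be a concern. The documents support calling it a named safety endpoint and no more.

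The reply does not supply the missing displays. Totals without terms do not show which events differ between arms, event counts do not give the number of patients affected, and figures derived after unblinding are not the pre-specified analysis that SAP section 1 says the plan is meant to provide.

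**Conclusion.** The point holds as a mismatch between the safety endpoints and the planned tables. There are 39 general TEAE and SAE tables by period and none for the whole study by term; the only by-term tables not split by period are the two on discontinuations. The viral-infection endpoint has no table that pools viral terms. Followed exactly, the SAP does not tabulate first-dose-to-Week-36 incidence per term by arm, and the period tables can only bound it, sometimes widely (9.0% to 30.3% in the assumed example).

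This rests on reading the table list in SAP 10.1 as complete. The numerical illustrations depend on assumed counts, assumed rates and a constant hazard, and show the mechanism rather than an expected result. Efficacy conclusions, error rates and data collection are unaffected. It should be corrected because it concerns the trial's main safety display and costs very little to put right.

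**What to change.** Add whole-study versions, from first dose to Week 36 or early termination and by arm, of the TEAE and SAE tables by SOC/PT, with the relationship and intensity versions from the same programs. That is 3 + 3 = 6 tables. Count each patient once per term, and state how a patient with several occurrences is classified for intensity and relationship. Keep the period tables as supportive.

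Add one viral-infection table by arm and severity, with the list of MedDRA terms that count as viral fixed before unblinding. A risk difference with confidence interval is optional; SAP 5.1.2 already names the score method for binary endpoints.

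If the sponsor prefers period tables only, SAP 7.3 should declare and justify this as a change from Protocol 13.9.5.

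The cost is a short SAP edit, seven table entries (6 + 1), reruns of existing programs without the period filter, and agreement on the viral term list. No new data are needed.

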5.2.5.3 Laboratory safety variables

Laboratory evaluations will be summarized by visit and by treatment group on the Safety population.

For each hematology, chemistry and coagulation variables:

- Quantitative descriptive statistics will be tabulated at each visit over the course of the study for raw values and change from baseline (Statistical tables 14.3.15.1, 14.3.15.2, 14.3.16.1, 14.3.16.2, 14.3.17.1, 14.3.17.2.)
- Qualitative descriptive statistics will be tabulated for each laboratory variable at each time over the course of the study:
 - By clinical significance (normal, Abnormal CS/N, Abnormal CS/AE, Abnormal NCS) (Statistical tables 14.3.15.3, 14.3.16.3, 14.3.17.3)
 - by grade (if applicable) (Statistical tables 14.3.15.4, 14.3.16.4, 14.3.17.4)

All urinalysis parameters will also be analyzed as quantitative variables (Statistical table 14.3.18)

In addition, the incidence of severe infections based on the total T-lymphocyte count (lymphocytes < 1000 versus lymphocytes > 1000/mm³) at the visit 2 (D0) will be presented (Statistical table 14.3.19).

Statistical Analysis Plan

Study Name: IFN-K-002

SAP version & date: v4, 18/Jun/2018

All laboratory results will also be presented in Listings 16.2.8.1 to 16.2.8.3.

Urine analysis data will be listed in Listing 16.2.8.4.

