13.4 Safety Endpoints

- Occurrence, intensity and relationship of any solicited local and systemic AEs during a 7-day follow-up period (i.e. day of study product administration and 6 subsequent days) after each IFN-K or placebo dose
- Occurrence, intensity and relationship of unsolicited local and systemic AEs occurring throughout the study period
- Occurrence and relationship of all SAEs occurring throughout the study period
- Occurrence and intensity of solicited local reactions 1 hour post study product administration
- Occurrence and intensity of solicited systemic reactions 1 hour post study product administration
- Hematological and biochemical levels within or outside the normal ranges and percent change from baseline at each visit
- Occurrence, intensity and relationship of any abnormality in physical examination, vital signs, 12-lead ECG, clinical laboratory evaluations
- Rate and severity of viral infections

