4.2.2 Laboratory endpoints

The following clinical laboratory tests are to be performed on collected blood samples:

- Clinical chemistry: Alanine Aminotransferase (ALT), Aspartate Aminotransferase (AST), Alkaline phosphatase, Creatine phosphokinase (CPK), Creatinine, Urea, Total proteins, Albumin, Circulating Anti-Coagulant
- Hematology: Complete blood cell count and differential (RBC, WBC, Lymphocytes, Neutrophils, Platelets); CD19; Total lymphocytes, CD4+, CD8+, Hemoglobin
- Coagulation: INR, Prothrombin time (PT), Partial Thromboplastin Time (PTT), Fibrinogen, Coomb's test (direct)
- Urine: RBC, WBC, Urinary casts, Albumin, Creatinine, Protein concentration, Albumin/Creatinine ratio, Protein/Creatinine ratio
- Dipstick Urinalysis: pH, glucose, etc

Hematology, clinical chemistry, coagulation and urine analysis data will be graded at each scheduled assessment by Modified WHO Toxicity Scale (See Protocol Appendix 10).

Hematological, clinical chemistry and coagulation safety will be based at each visit on raw value, percent change from baseline and categories (grade or normal, Abnormal CS/N, Abnormal CS/AE, Abnormal NCS).

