5.2.1 Demographics and baseline characteristics

The following demographics variables will be summarized by treatment group on the SAF and then in the FAS, if the two analysis sets are different. (Statistical table 14.1.4):

- Age (continuous and class [18-40], [41-65])
- Gender
- Ethnic origin (see section 9 Derived data)
- Presence or absence of renal BILAG at screening
- With or without CS treatment at randomization
- With or without HCQ treatment at randomization
- With or without MMF treatment at randomization
- With or without MTX treatment at randomization
- With or without AZA treatment at randomization

The following baseline characteristics will be summarized by treatment group on the FAS set:

- Alcohol, drug and tobacco use (Statistical table 14.1.5)
- Vital signs at baseline (Statistical table 14.1.6)
- ECG at baseline (Statistical table 14.1.7)
- Physical examination (including Weight, Height and BMI) at baseline (Statistical table 14.1.8)

Statistical Analysis Plan

Study Name: IFN-K-002

SAP version & date: v4, 18/Jun/2018

- Laboratory test: Haematology (Statistical table 14.1.9), clinical chemistry (Statistical table 14.1.10), Coagulation (Statistical table 14.1.11) and Urinalysis (Statistical table 14.1.12) at baseline
- Laboratory test abnormalities (grade or normal, Abnormal CS/N, Abnormal CS/AE, Abnormal NCS): Haematology abnormalities (Statistical table 14.1.13), Chemistry abnormalities (Statistical table 14.1.14), Coagulation abnormalities (Statistical table 14.1.15) and Urinalysis abnormalities (Statistical table 14.1.16) at baseline
- Viral serology, autoantibodies and inflammatory markers at baseline
- Gynecological examination (Cytological examination and HPV on PAP smear) (Statistical table 14.1.20)
- Efficacy variable at baseline (IFN score, SLEDAI-2K score, BILAG global score, SELENA-SLEDAI flare index, CLASI, SLICC/ACR-DI, PGA score, 28-Tender and Swollen Joint Counts, Joint Pain VAS, SF-36 (Physical Component Summary (PCS) and Mental Component Summary (MCS) scores), FACIT (Statistical table 14.1.21)

All demographics data, Alcohol, drug and tobacco use data and gynecological examination data of each patient will be reported in listing 16.2.4.1, 16.2.4.2 and 16.2.4.3 respectively.

Viral serology and pregnancy test data will be listed in Listing 16.2.4.10 and 16.2.4.11.

The definition of baseline is provided in section 5.4.1.

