14.3.12.4	SAEs by SOC, PT and relationship - Period [3rd dose; 4th dose[X			
14.3.12.5	SAEs by SOC, PT and relationship - Period [4th dose; 5th dose[X			
14.3.12.6	SAEs by SOC, PT and relationship - Period [5th dose; Week 36]		X			
14.3.12.7	SAEs by SOC, PT and relationship - Period [Last dose; Week 36/Early Termination]		X			
14.3.13.1	SAEs by SOC, PT and intensity - Before 1st dose		X			
14.3.13.2	SAEs by SOC, PT and intensity - Period [1st dose; 2nd dose[X			
14.3.13.3	SAEs by SOC, PT and intensity - Period [2nd dose; 3rd dose[X			
14.3.13.4	SAEs by SOC, PT and intensity - Period [3rd dose; 4th dose[X			
14.3.13.5	SAEs by SOC, PT and intensity - Period [4th dose; 5th dose[X			
14.3.13.6	SAEs by SOC, PT and intensity - Period [5th dose; Week 36]		X			
14.3.13.7	SAEs by SOC, PT and intensity - Period [Last dose; Week 36/Early Termination]		X			
14.3.14	SAEs leading to permanent study drug discontinuation by SOC and PT		X			
14.3.15.1	Hematology - Value at each visit		X			
14.3.15.2	Hematology - Change from baseline		X			
14.3.15.3	Hematology - Abnormalities at each visit		X			
14.3.15.4	Hematology - Grade at each visit		X			
14.3.16.1	Chemistry - Value at each visit		X			
14.3.16.2	Chemistry - Change from baseline		X			
14.3.16.3	Chemistry - Abnormalities at each visit		X			
14.3.16.4	Chemistry - Grade at each visit		X			
14.3.17.1	Coagulation - Value at each visit		X			
14.3.17.2	Coagulation - Change from baseline		X			
14.3.17.3	Coagulation - Abnormalities at each visit		X			

Statistical Analysis Plan

Study Name: IFN-K-002

SAP version & date: v4, 18/Jun/2018

Number	Title	Screened	SAF	FAS	PP	Other
14.3.17.4	Coagulation - Grade at each visit		X			
14.3.18	Urinalysis - Value at each visit		X			
14.3.19	Incidence of severe infections at D0		X			
14.3.20.1	Weight and BMI - Value at each visit		X			
14.3.20.2	Weight and BMI - Change from baseline		X			
14.3.21	Physical examination, Body system at each visit		X			
14.3.22.1	Vital signs - Value at each visit		X			
14.3.22.2	Vital signs - Change from baseline		X			
14.3.23	ECG - Abnormalities at each visit		X			
14.3.24	Concomitant medications		X			

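### Post-baseline urine results are to be WHO-graded at every assessment, but the SAP tabulates them only as raw values, so new or worsening proteinuria or haematuria is not counted by arm from the laboratory data

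*SAP*

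**What the plan says.** SAP 4.2.2 sets the grading rule: "Hematology, clinical chemistry, coagulation and urine analysis data will be graded at each scheduled assessment by Modified WHO Toxicity Scale". The sentence that follows, on what laboratory safety rests on, leaves urine out: "Hematological, clinical chemistry and coagulation safety will be based at each visit on raw value, percent change from baseline and categories".

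SAP 5.2.5.3 introduces its value, change, clinical-significance and grade tables with "For each hematology, chemistry and coagulation variables". Urine is handled separately: "All urinalysis parameters will also be analyzed as quantitative variables (Statistical table 14.3.18". Listing 16.2.8.4 adds patient-level urine data.

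In SAP 10.1, table 14.3.18 is titled "Urinalysis - Value at each visit". By contrast, table 14.3.15.4 is "Hematology - Grade at each visit", and chemistry and coagulation have the same. SAP 5.2.1 does tabulate urine abnormalities in categories, but only once: "Urinalysis abnormalities (Statistical table 14.1.16) at baseline".

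The safety endpoint in Protocol 13.4 is "Occurrence, intensity and relationship of any abnormality in physical examination, vital signs, 12-lead ECG, clinical laboratory evaluations".

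**The concern.** A grade that is assigned but never tabulated does not inform the safety comparison. The protocol endpoint asks how often abnormalities occur and how intense they are. Raw urine values by visit answer neither question as a count of patients, and without change from baseline or a shift they do not separate a patient with stable urine protein from one whose urine protein is new or rising.

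This matters more for urine than for most panels. Protocol 8.3.2 excludes renal BILAG A, but patients with lesser renal involvement can enter, and presence of renal BILAG at screening is a minimisation factor (Protocol 9.2.2). Protocol Table 4 makes corticosteroid tapering mandatory in the maintenance period. A reader of the safety report will want to know how many patients in each arm developed or worsened proteinuria or haematuria.

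**Working it through.** No power, alpha or event figure bears on this point. The check sets the sections side by side and counts tables and visits.

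**1. Planned post-baseline tables (SAP 5.2.5.3 and 10.1).**

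| Panel | Value | Change from baseline | Clinical significance | WHO grade | Total |
|---|---|---|---|---|---|
| Haematology | 14.3.15.1 | 14.3.15.2 | 14.3.15.3 | 14.3.15.4 | 4 |
| Chemistry | 14.3.16.1 | 14.3.16.2 | 14.3.16.3 | 14.3.16.4 | 4 |
| Coagulation | 14.3.17.1 | 14.3.17.2 | 14.3.17.3 | 14.3.17.4 | 4 |
| Urinalysis | 14.3.18 | none | none | none | 1 |

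The other three panels have 4 + 4 + 4 = 12 tables; urine has 1. The word *also* in SAP 5.2.5.3 might suggest that a categorical urine analysis exists elsewhere. The table list contains none after baseline.

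**2. Visits affected.** Protocol 10.9 schedules urinalysis at Weeks 0, 4, 8, 12, 16, 20, 24, 28, 32 and 36, which is 10 visits, of which 10 − 1 = 9 are post-baseline. At none of the nine is a grade, clinical-significance or change table planned for urine.

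**3. Whether the data exist.** Protocol 12.1.2 has laboratory abnormalities graded on the WHO scale and classed by the site as NCS, CS/N or CS/AE. Baseline table 14.1.16 already uses such categories for urine. SAP 4.2.2 lists urine red and white cells, casts, albumin, creatinine, protein and the two creatinine ratios. Protocol Appendix 10 has a proteinuria row and a haematuria row.

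**4. Whether the change is declared.** SAP 7.4 reports one laboratory modification, the replacement of percent change by change. It does not mention urine.

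**5. What reaches an arm comparison by another route.**
- *AE tables.* Under Protocol 12.1.2 a urine finding becomes an AE only if it is clinically significant and not normal for the study population. It is then counted by arm (SAP 5.2.5.2). NCS and CS/N findings are not.
- *BILAG shift table 14.2.11.* This gives one composite renal grade, at the last available value of Week 24 or Week 36. It can miss transient worsening and does not isolate proteinuria or haematuria.
- *Flare summaries.* New or worse nephritis counts towards a severe SELENA-SLEDAI flare (table 14.2.13), and time to first flare uses BILAG A or B scores from new or worse items. Both are composites.
- *SLEDAI-2K.* Proteinuria, haematuria, casts and pyuria are scored, but SAP 5.2.4.3.2 summarises the total and the response, not the items.
- *Listing 16.2.8.4.* Patient level only.

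No route counts all patients with new or worsening proteinuria or haematuria by arm.

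**The case against.** The strongest reply is that SAP 5.2.5.3 follows the second of the two sentences in SAP 4.2.2, which omits urine, so the plan may intend exactly what it lists. That locates the conflict inside SAP 4.2.2. It does not resolve it, because the first sentence still promises a urine grade at each assessment that nothing reports.

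A second reply is that Protocol 13.9.5 plans no urine grade table, so SAP 7.4 had nothing to declare. This weakens the complaint about non-declaration. That complaint then rests on the endpoint in Protocol 13.4, which covers clinical laboratory evaluations, and Protocol Table 6 includes urine testing among the laboratory assays.

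A third is that relationship, part of that endpoint, is an AE attribute, and the AE tables report occurrence, intensity and relationship by arm. This stands for CS/AE findings. A reader might infer that new renal disease would go uncounted altogether; the documents do not support that, given the AE, BILAG and flare routes. Nor is table 14.3.18 a bare mean: SAP 5.1.1 requires the median, quartiles, minimum and maximum, so a large shift between arms could still be visible. It would not be a patient count.

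A reader might also infer from the eligibility rules and the minimisation factor that many patients start with urine abnormalities. The documents give no figure.

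Finally, the WHO rows do not map cleanly onto the data. Haematuria grades 2 to 4 depend on gross blood, clots or transfusion, which microscopy and dipstick cannot establish, and proteinuria grade 0 is defined as no change. This limits the form of the remedy, not the need for one.

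**Conclusion.** The point holds in a limited form. SAP 4.2.2 promises graded urine data, and SAP 5.2.5.3 and 10.1 deliver raw values in one table, against four tables for each other panel, across nine post-baseline visits. The protocol endpoint of occurrence and intensity of any laboratory abnormality is therefore not met from the urine results. What goes uncounted is urine findings classed NCS or CS/N, together with any count specific to proteinuria or haematuria that the composites absorb. How many patients this involves cannot be stated from the documents.

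The conclusion assumes that SAP 10.1 is the complete list of planned tables and that sites classify urine results as Protocol 12.1.2 requires. This is a safety-reporting gap that should be closed; the primary and secondary efficacy analyses are unaffected.

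**What to change.** In SAP 5.2.5.3 and 10.1, add post-baseline urinalysis tables by arm on the safety population, numbered beside 14.3.18:

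- clinical-significance category at each visit;
- change from baseline for the quantitative parameters, for example the protein/creatinine ratio;
- worst post-baseline WHO proteinuria grade, with a shift from the baseline category in 14.1.16, stating how baseline is categorised given that grade 0 means no change;
- haematuria as present or absent, or by clinical significance, with a shift from baseline, using the WHO grade only where clinical information allows it;
- casts and dipstick results as categories.

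If the sponsor does not want these tables, the minimum is to correct the grading sentence in SAP 4.2.2 and record the omission in SAP 7.4. That would remove the inconsistency but leave the Protocol 13.4 endpoint unmet for urine.

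The cost is a few extra tables and one baseline-category definition. No new data collection is needed.
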